**The Effect of Perioperative Heated Sock Use in Preventing Hypothermia During Total
Hip Prosthesis Surgery: A Randomized Controlled Trial**

NCT number: NO

Document Date:31/12/2022

Methods

Study Aim and Design

The aim of the study was to determine the effect of one of the active heating methods of perioperative heated sock use to prevent hypothermia during THP surgery and to contribute to the literature. This study is a randomized, controlled experimental study.

Population and Sampling

The population for the research comprised patients undergoing THP surgeries between 15 October 2021 and 31 December 2022 in Samsun Gazi State Hospital. The sample for the population comprised patients who met the research criteria and who accepted participation in the research from among individuals in the population. Calculation of the effect size in the study used the calculation method (d value) developed by Cohen (Cheon & Yoon, 2017). To determine the d value for the effect size index, findings from studies researching the effect of perioperative heating on preventing hypothermia by Lee et al. (2018) and Lau et al. (2018) were used. In the calculations for these studies, the effect size obtained from comparing two groups was identified to be $d=1$ and above (large effect). However, with the aim of obtaining a larger sample group in this research, it was appropriate to take large effect size as reference for the initial limit for the t test to measure the difference between two groups. In this context, with $d=0.8$, $\alpha=0.05$ (error), $1-\beta=0.95$ (power), accompanied by the stated criteria, with the aid of the G-power (version 3.1) program, the sample group was determined to require a total of 70 people, with 35 in the experiment group and 35 in the control group.

Data collection instruments and procedure for data collection

This research was completed in the orthopedic clinic ward, preoperative waiting unit, operating rooms, and post-anesthesia care unit (PACU) in a public hospital in Samsun, during daily working hours of 08:00-16:00. Data were collected with a Descriptive Features Form,

Recording Form for Measured Data, tympanic thermometer and blood pressure device. Six heated socks and a thermal blanket were used during the intervention.

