Heated Socks: In the research, 6 heated socks (operated with rechargeable batteries) obtained by the researchers were used. Socks used sequentially by each patient were sterilized in the hospital's sterilization unit and then worn. Each pair of socks worked with 6 rechargeable batteries. Heated socks are a non-invasive, easily worn, pain-free and suitable-cost method to prevent heat loss (Lee, 2018).

Both verbal and written consent was obtained from patients accepting participation in the research. Firstly patients completed the Descriptive Features Form. Then 75 minutes before surgery, patients in the experiment group were dressed in heated socks in the orthopedic ward. Before dressing in heated socks and every fifteen minutes afterwards, body temperature, heart rate, blood pressure and shivering were measured and recorded for each patient.

During transfer from the orthopedic ward to the surgery, a thermal blanket was used to prevent temperature loss. The patient was transferred to the surgery with the heated socks and the socks remaining on the feet during surgery. In the first fifteen minutes until taken from the preoperative waiting unit to the operating room and every fifteen minutes during a total of 120 minutes of surgery, body temperature, blood pressure and shivering were monitored and recorded. Additionally, the total drainage amount was recorded during surgery. When surgery ended, the patient was transferred to the PACU with the socks and the socks remained on the patient's feet while in the PACU. In the PACU, the body temperature, heart rate, blood pressure, shivering and total drainage amount were measured and recorded every fifteen

minutes for a total of thirty minutes. During transfer from the surgery to the orthopedic ward, a thermal blanket was used to prevent temperature loss in patients. Patients were transferred from PACU to the ward with the socks.

The socks remained on the feet for 3 hours after returning to bed postoperatively. After transfer to the bed and every fifteen minutes, body temperature, heart rate, blood pressure, and shivering were measured and recorded for a total of 180 minutes. Additionally, patients had 24-hour total drainage amounts measured and recorded. Patients in the control group underwent the same procedures as patients in the experiment group. The only difference was that patients in the experiment group were dressed in heated socks, while patients in the control group were not dressed in heated socks.

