**The Effect of Perioperative Heated Sock Use in Preventing Hypothermia During Total
Hip Prosthesis Surgery :A Randomized Controlled Trial**

NCT number: NO

Document Date:31/12/2022

Population and Sampling

The population for the research comprised patients undergoing THP surgeries between 15 October 2021 and 31 December 2022 in Samsun Gazi State Hospital. The sample for the population comprised patients who met the research criteria and who accepted participation in the research from among individuals in the population. Calculation of the effect size in the study used the calculation method (d value) developed by Cohen (Cheon & Yoon, 2017). To determine the d value for the effect size index, findings from studies researching the effect of perioperative heating on preventing hypothermia by Lee et al. (2018) and Lau et al. (2018) were used. In the calculations for these studies, the effect size obtained from comparing two groups was identified to be $d=1$ and above (large effect). However, with the aim of obtaining a larger sample group in this research, it was appropriate to take large effect size as reference for the initial limit for the t test to measure the difference between two groups. In this context, with $d=0.8$, $\alpha=0.05$ (error), $1-\beta=0.95$ (power), accompanied by the stated criteria, with the aid of the G-power (version 3.1) program, the sample group was determined to require a total of 70 people, with 35 in the experiment group and 35 in the control group.

Data analysis

The SPSS program was used for statistical analysis. The Kolmogorov Smirnov test was used to show whether data obtained from the groups had normal distribution or not. The independent samples T test and Mann-Whitney U test were used for comparisons between two groups of quantitative data. The one-way analysis of variance, or the non-parametric equivalent of the Kruskal-Wallis test, were used for comparisons of more than two groups. To test the differences in repeated measures, the paired samples test was used for data with normal distribution and the Wilcoxon test was used for data without normal distribution. Qualitative comparisons between groups used the Pearson chi-square or Fisher exact chi-square tests. Additionally, multiple linear regression modelling was used to measure the effect

of the independent variables on the dependent variable. Results were analyzed in the 95% confidence interval with $p<0.05$ indicating significance.

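### The SAP names no decisive temperature comparison among 22 or more scheduled readings and no multiplicity rule, and its only repeated-measures test describes change within patients, not the sock effect

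*SAP*

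**What the plan says.** The aim, in the protocol's Study Aim and Design section, is to find the effect of "perioperative heated sock use to prevent hypothermia during THP surgery".

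The protocol's data collection section sets out dense readings. On the ward before the operation: "Before dressing in heated socks and every fifteen minutes afterwards, body temperature, heart rate, blood pressure and shivering were measured". In theatre: "every fifteen minutes during a total of 120 minutes of surgery, body temperature, blood pressure and shivering were monitored and recorded". Body temperature is also taken every 15 minutes for 30 minutes in the PACU. Back on the ward: "After transfer to the bed and every fifteen minutes, body temperature, heart rate, blood pressure, and shivering were measured and recorded", for 180 minutes.

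The SAP's Data analysis section lists tests by type of data:
- Between arms: "The independent samples T test and Mann-Whitney U test were used for comparisons between two groups of quantitative data".
- Repeated readings: "To test the differences in repeated measures, the paired samples test was used for data with normal distribution", with the Wilcoxon test for non-normal data.
- Yes/no data: chi-square or Fisher tests.
- A multiple linear regression whose dependent and independent variables are not named.
- The decision rule for all of these: "Results were analyzed in the 95% confidence interval with $p<0.05$ indicating significance".

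Neither document names a primary outcome, a decisive reading or window, a per-patient summary, or an adjustment for multiple tests.

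**The concern.** The randomised question is how temperature differs between patients with and without the socks. The plan contains a test that can answer it, but does not say what that test is applied to. With temperature measured at least 22 times during and after surgery, the analyst may choose any reading, every reading, a mean, a lowest value or a change, and each choice is judged at p<0.05. A difference at any one reading could then be presented as the effect.

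The one method assigned to the repeated readings does not fill this gap. A paired or Wilcoxon test compares a patient with himself or herself. In the sock arm it measures the course over time plus any sock effect; in the control arm it measures the course over time alone. The sock effect is the difference between those two changes, and neither test evaluates that difference. Reporting that one arm changed significantly and the other did not would be a misleading substitute.

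The pre-sock temperature is collected in every patient but has no stated role in comparing the arms.

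**Working it through.** **1. The plan's own figure.** Inputs from Population and Sampling: d = 0.8, alpha = 0.05, power = 0.95, 35 per arm, one two-group t test. The noncentrality is d × √(n/2) = 0.8 × √17.5 = 3.35, with 68 df.
- One-sided: power 0.952, and 35 per arm is the smallest sufficient number. The stated total of 70 is reproduced.
- Two-sided: power 0.910; reaching 0.95 would need 42 per arm.

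The trial is therefore sized for one between-arm comparison, which the SAP does not identify. (The unstated sidedness is a separate matter.)

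**2. Number of readings.** Surgery 120/15 = 8; PACU 30/15 = 2; ward 180/15 = 12. Total 22. A reading on arrival in bed would make the ward count 13. Adding about 4 to 5 preoperative readings after the socks go on, and 1 in the waiting unit, gives about 27 to 29 post-baseline readings. The calculations below use 10 (surgery plus PACU) and 22.

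**3. Which listed methods can give the sock-versus-control contrast in temperature.**

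| Method in the SAP | Between-arm contrast? |
|---|---|
| Independent t / Mann-Whitney | Yes, once a reading or summary is named |
| Paired / Wilcoxon | No; change within patients |
| One-way ANOVA / Kruskal-Wallis | For more than two groups; the trial has two arms |
| Multiple linear regression | Unknown; variables not named |
| Chi-square / Fisher | Only for hypothermia as yes/no, also tied to no reading |

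**4. False-positive chance if the t test is run at every reading.** The documents give no within-patient correlation, so a range is assumed. Simulation with no sock effect: multivariate normal readings, 35 per arm, two-sided 0.05 at each reading, 40,000 replicates per setting (Monte Carlo SE at most 0.0025). Chance of at least one p<0.05:

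| Assumed correlation | 10 readings | 22 readings |
|---|---|---|
| Constant 0.9 | 0.127 | 0.159 |
| Constant 0.8 | 0.175 | 0.237 |
| Constant 0.7 | 0.214 | 0.304 |
| Constant 0.5 | 0.288 | 0.442 |
| AR(1) 0.95 per 15 min | 0.142 | 0.234 |
| AR(1) 0.90 | 0.188 | 0.331 |
| AR(1) 0.80 | 0.258 | 0.458 |

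Over the 8 surgery readings alone, constant correlation 0.9 to 0.5 gives 0.119 to 0.251. Counting only false positives that favour the socks, the ranges are 0.06 to 0.15 over 10 readings and 0.08 to 0.24 over 22, against 0.025 for one prespecified two-sided test.

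**5. Why within-arm significance is no substitute.** Give both arms the same true standardised change and no sock effect. With 35 patients, let p be the power of the paired t test in each arm. The chance that exactly one arm is significant is 2p(1 − p):
- change 0.2: p = 0.210, chance 0.33
- change 0.33: p = 0.475, chance 0.50
- change 0.5: p = 0.820, chance 0.30
- change 0.8: p = 0.996, chance 0.01

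These standardised changes are assumptions.

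**6. What adjusting for the pre-sock reading buys.** The approximate 95% CI half-width is t × √(2/35) × SD, with t = 1.995, so 0.477 × SD. For the mean of 10 readings under constant correlation ρ, the SD is √((1+9ρ)/10) unadjusted and √((1+9ρ)/10 − ρ²) adjusted, in units of the SD of one reading.
- ρ = 0.5: 0.354 falls to 0.261.
- ρ = 0.8: 0.432 falls to 0.202.
- AR(1) 0.80, readings 6 to 15 steps after baseline: 0.351 falls to 0.347.
- AR(1) 0.95, same steps: 0.440 falls to 0.338.

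The gain runs from about 1% (0.004/0.351) to about 53% (0.230/0.432).

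**The case against.** The strongest reply is that the plan already contains a valid test. An independent t or Mann-Whitney test on any sensible temperature summary estimates the sock effect without bias under randomisation. That stands: the fault is an unnamed comparison, not the absence of a between-arm test. A reader might infer that the SAP cannot compare the arms on temperature, and the text does not support that.

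Nor does the SAP say that the paired test is meant to show the sock effect. As a description of change over time it is legitimate. What stands is a warning about how its results may be read.

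The false-positive figures are conditional. The SAP does not say that every reading will be tested, or that one significant reading will be reported as the effect. It leaves both open.

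A reader might also infer that the pre-sock reading goes unused. That is not shown: it may enter the paired tests, and the regression covariates are unnamed rather than stated to exclude it. The regression may include study group too, but with no named variables it commits the analyst to nothing.

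Finally, a window mean can hide a brief fall in temperature. That limitation is real, and is why any yes/no analysis of hypothermia should use the same window.

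**Conclusion.** The point holds as a fault of specification with a real consequence for error control. No temperature reading, window or summary is decisive, every test is judged at p<0.05, no multiplicity rule is given, and the only repeated-measures method cannot supply the randomised contrast.

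If every reading were tested and any single hit reported, the false-positive chance would be about 0.13 to 0.29 over 10 readings and 0.16 to 0.46 over 22, instead of 0.05. This rests on assumed correlations (constant 0.9 to 0.5, or AR(1) 0.95 to 0.80), normal readings, complete data and 35 per arm. Even the most favourable setting over 10 readings is more than double the nominal level.

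Two further inferences should be resisted. Power is not the problem: one two-sided t test at the plan's d = 0.8 has power 0.91. And an unadjusted comparison is not invalid; baseline adjustment serves precision and chance imbalance, with a gain that may be negligible or substantial.

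**What to change.** For body temperature, make one between-group comparison decisive. Take each patient's mean over one stated window and compare the arms by ANCOVA adjusted for the pre-sock reading (the same time point in controls). Report one difference with its 95% CI. The 8 surgery readings fit the stated aim most literally; surgery plus PACU is acceptable if stated.

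- A linear mixed model with the same adjustment is an option, useful if readings are missing.
- If residuals are clearly non-normal, use a rank-based or bootstrap version of the same contrast.
- Treat the preoperative, waiting-unit and ward readings, and the within-arm paired or Wilcoxon results, as secondary or descriptive, not as evidence of the sock effect.
- If hypothermia as yes/no is analysed by chi-square or Fisher, define it once per patient over the same window.

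The cost is SAP wording and a little more analysis work, with no new data. The SAP is dated 31/12/2022, the last day of the stated study period, so the change must be dated, and labelled post hoc if made after the data were seen.

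### The SAP applies p<0.05 to every result and fixes no primary outcome, time point, hypothermia definition or multiplicity rule, so the 5% error rate attaches to no stated comparison

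*SAP*

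**What the plan says.** The protocol's aim (Study Aim and Design) concerns "perioperative heated sock use to prevent hypothermia during THP surgery". In Population and Sampling, the effect size is drawn from "findings from studies researching the effect of perioperative heating on preventing hypothermia", and d=0.8 is applied to a two-group t test without naming the variable.

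Under its data collection heading, the protocol schedules repeated measurement. On the ward: "Before dressing in heated socks and every fifteen minutes afterwards, body temperature, heart rate, blood pressure and shivering were measured". In theatre: "every fifteen minutes during a total of 120 minutes of surgery, body temperature, blood pressure and shivering were monitored and recorded". Quarter-hourly temperature readings continue for 30 minutes in the PACU and 180 minutes back on the ward.

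The SAP's Data analysis section lists tests by type of data, not by outcome. Between arms: "The independent samples T test and Mann-Whitney U test were used for comparisons between two groups of quantitative data". For repeated readings: "To test the differences in repeated measures, the paired samples test was used for data with normal distribution", with the Wilcoxon test otherwise. A multiple linear regression is mentioned, but its dependent variable is not identified. The closing rule covers everything: "Results were analyzed in the 95% confidence interval with $p<0.05$ indicating significance".

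**The concern.** The aim and the source of the effect size point to hypothermia during surgery. Neither document says whether that means temperature or hypothermia yes/no, at what threshold, or at which reading or over which period. Paired and Wilcoxon tests compare a patient with him- or herself, so they cannot deliver the treatment comparison. The named between-group tests are attached to no outcome and no time. The plan therefore permits a between-group temperature test at any reading, each at 5%, besides tests of blood pressure, heart rate, shivering and drainage.

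Two things are at stake. A reader cannot tell which result the trial's conclusion rests on. And if several readings are tested and any significant one is taken as an effect, the chance of a false claim exceeds the nominal 5%.

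**Working it through.** **1. The plan's own figure.** Inputs from Population and Sampling: d=0.8, alpha=0.05, power 0.95, 35 per arm. The noncentrality is 0.8 × √(35/2) = 3.35 on 68 degrees of freedom. An exact one-sided t test has 95.2% power, and 35 is the smallest arm size that reaches 95%, so the total of 70 reproduces. An exact two-sided test at 35 per arm has 91.0% power and would need 42 per arm (84 in total). The documents do not state sidedness.

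**2. Number of readings.** From the protocol's schedule, after the pre-sock reading:

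| Phase | Calculation | Readings (upper count adds a reading at the start of the phase) |
|---|---|---|
| Ward before surgery | 75/15 | 5 |
| Waiting unit | – | 0 to 1 |
| Surgery | 120/15 | 8 to 9 |
| PACU | 30/15 | 2 to 3 |
| Ward after surgery | 180/15 | 12 to 13 |
| Total | | 27 to 31 |

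**3. Limits for 8 surgery readings, each tested at 5%.** With perfect correlation the 8 tests are one test: 5%. With independence: 1 − 0.95^8 = 0.337. These limits need no correlation estimate.

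**4. Between the limits.** The documents give no correlation between readings, so the values below are assumptions. Simulation with no true effect: normal data, 35 per arm, two-sided t test at each of 8 readings, 30,000 trials per setting. The Monte Carlo standard error near 22% is √(0.22 × 0.78/30,000) = 0.0024. Chance of at least one p<0.05:

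| Equal correlation | 0.98 | 0.95 | 0.9 | 0.8 | 0.7 | 0.6 | 0.5 |
|---|---|---|---|---|---|---|---|
| Chance | 7.9% | 9.7% | 12.1% | 15.7% | 19.8% | 22.5% | 25.2% |

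If correlation instead decays with time (first-order autoregressive), the chance is 8.0% at an adjacent correlation of 0.99, 12.3% at 0.95, 16.1% at 0.9 and 21.3% at 0.8. With 9 readings, equal correlations of 0.98 to 0.6 give 7.7% to 24.2%.

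**5. Whole schedule.** For 28 readings (normal approximation), equal correlation gives 9.2% at 0.98, 16.8% at 0.9 and 24.8% at 0.8. The autoregressive form gives 27.5% at 0.95 and 39.2% at 0.9. Independence gives 1 − 0.95^28 = 0.762.

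**6. Would one summary test repair it?** A single two-sided, baseline-adjusted test of each patient's mean over 8 surgery and 2 PACU readings was simulated under five correlation settings (10,000 trials each): equal 0.98, autoregressive 0.95 and 0.8, and two that combine a patient effect with autoregression. Its type I error was 4.7% to 5.5%. Its power was 99% or more if d=0.8 held at every post-baseline reading, and 60% to over 99% if d=0.8 appeared only in the last 5 of the 10 readings. The mean over surgery readings alone was not simulated.

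**The case against.** The strongest reply is that no percentage here is a property of the plan. The SAP does not say that arms are compared at each reading, nor that one significant reading would be taken as success. The t test could be applied to one summary per patient, or the regression could be the main analysis. This stands, and it is why the range is conditional. It does not rescue the plan, because neither document says that such a summary or model is the primary analysis.

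Sidedness is also assumed. The figures use two-sided tests, whereas 70 patients reproduces only with a one-sided test. This stands too. With one-sided 5% tests, a false result in the socks' favour over 8 readings would occur in about 7.3% to 19.2% of trials, against 5% for one test. The inflation remains, with different figures.

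Three stronger readings are tempting but unsupported:

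- That this trial's false-positive rate is 22%. That needs reading-by-reading testing, an any-significant-reading rule and a particular correlation, none of which is in the documents.
- That 22% is a ceiling. Equal correlation of 0.5 already gives 25.2%, and independence gives 33.7%.
- That the outcome was chosen after seeing the data. Both documents are dated 31/12/2022, the last day of the surgery window ("The population for the research comprised patients undergoing THP surgeries between 15 October 2021 and 31 December 2022"). That leaves the timing open and proves nothing about it.

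**Conclusion.** The omission is certain and does not depend on any simulation: no primary outcome, time point, hypothermia definition or multiplicity rule is given, and no stated method turns the repeated readings into one comparison between arms. The aim shows the topic but does not fix an endpoint.

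The size of the inflation is conditional. The range of about 8% to 22% holds if all 8 surgery readings are compared between arms, tests are two-sided, any p<0.05 is claimed as an effect, and readings correlate equally at about 0.98 down to 0.6. Confidence is high in the gap and moderate in the figure. The plan should be corrected. The data as scheduled can support a single well-defined test, so the design itself is not defeated.

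**What to change.** Name one primary between-group comparison that matches the aim. One example is each patient's mean temperature over the surgery readings, adjusted for the reading taken before the socks, in a single test at 5%. Extend the window to the PACU only if the plan says so. If hypothermia yes/no is preferred as primary, name it and give the sponsor's own definition.

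State the sidedness. If two-sided, acknowledge that 35 per arm gives 91% power for an unadjusted t test at d=0.8, not the stated 95%.

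Label all other time-point and outcome tests exploratory, and show the temperature curve as estimates with 95% intervals. If a few outcomes are kept as Holm-adjusted secondaries, fix one per-patient summary and window for each. Heart rate is not listed among the measurements during surgery, so its window must differ from that of temperature. Hypothermia as a secondary again needs the sponsor's own definition.

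Add a dated statement of when the primary was chosen, and report it as post hoc if group results had been seen. In that case the 5% rate is not restored.

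The cost is SAP wording, with no new data or patients. Fewer time-point results can be called significant. A period mean also dilutes an effect that appears only late: for the surgery-plus-PACU mean, power fell to about 60% in some settings.
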